5.1.1.1.4 Missing Data

No imputation of missing efficacy data for this study is specified for methodologies in Section 5.1.1.1.3.

5.1.1.1.5 Site Pooling

Unless specifically detailed, data will be pooled over sites for the summary analyses.

5.1.1.2 Demographics

The Screened Population, Safety, and mITT Populations will be used to summarize in this section.

5.1.1.2.1 Participant Disposition

Participant disposition encompasses the distribution of participants who enter, complete, and discontinue each specified analysis period, along with eCRF-reported discontinuation reasons from each respective analysis period. Participant disposition will be summarized as follows:

 Table 5-3
 Participant Disposition Summaries

Parameter	Description	Timing	Methodology
Screening and	Distribution in the screened population in	Screening Period	Continuous
disposition	total and by screen failure/screen success		descriptives and
_	• Age		categorical
	• Sex		descriptives
	• Ethnicity		
	Race group 1		
	o White		
	 Black or African American 		
	o Asian		
	 American Indian or Alaska 		
	Native		
	 Native Hawaiian or Other 		
	Pacific Islander		
	• Race group 2		
	o White		

Parameter	Description	Timing	Methodology
	 Non-white Reasons for screen failure in the screened population eCRF categories 		
Study disposition	Distribution in the safety population in total and by cohort (PK and Non-PK cohorts)	Treatment Period	Categorical descriptives

5.1.1.2.2 Protocol Deviations

Protocol deviations will be listed as follows:

Table 5-4 Protocol Deviations

Parameter	Description	Timing	Methodology
Important protocol	Protocol deviations are defined as any variation from the	_	Listing
deviations	protocol, including enrollment of a participant who did		
	not meet all inclusion criteria and/or met any exclusion		
	criteria and failure to perform the assessments and		
	procedures within the required time frame.		

5.1.1.2.3 Demographics

Demographics will be summarized in total and by cohort (PK cohort and Non-PK cohort) for the Safety Population, as follows:

Table 5-5 Demographic Summaries

Parameter	Description	Timing	Methodology
Age	Age (years) relative to informed consent	Informed consent	Continuous
	date		descriptives
Sex, ethnicity and race	• Sex	Screening Period	Categorical
	 Ethnicity 		descriptives
	Race group 1		
	o White		
	 Black or African 		
	American		
	o Asian		
	 American Indian or 		
	Alaska Native		
	 Native Hawaiian or 		
	Other Pacific Islander		
	• Race group 2		
	o White		
	 Non-white 		

5.1.1.2.4 Baseline Characteristics

Baseline characteristics will be summarized in total and by cohort (PK cohort and Non-PK cohort) for mITT or Safety Populations as follows:

Table 5-6 Baseline Characteristics Summaries

Parameter	Description	Timing	Methodology
Baseline characteristics	For Safety Population only:	Latest assessment in	Continuous
	Height (m)	Screening Period	descriptives
	• Weight (kg)		
	Body mass index (BMI)		
	• Weight (kg) / height (m) ²		
Baseline characteristics	For Safety Population only:	Latest assessment in	Categorical
	 Skin phototype assessment 	Screening Period	descriptives
	 I: Always burns easily; never 		
	tans (sensitive)		
	 II: Always burns easily; tans 		
	minimally (sensitive)		
	 III: Burns moderately; tans 		
	gradually (light brown)		
	(normal)		
	 IV: Burns minimally; always 		
	tans well (moderate brown)		
	(normal)		
	o V: Rarely burns; tans		
	profusely (dark brown)		
	(insensitive)		
	o VI: Never burns; deeply		
D: 1	pigmented (insensitive)	Ŧ	G 1
Disease characteristics	For mITT Population only:	Latest assessment in	Categorical
	Investigator's Global Assessment	Screening Period	descriptives
5	(IGA) (face only)	.	
Disease characteristics	For mITT Population only:	Latest assessment in	Continuous
	Total lesion counts (face only)	Screening Period	descriptives
	Inflammatory lesion counts (face)		
	only)		
	Non-inflammatory lesion counts		
	(face only)		

5.1.1.2.5 Medical History

Medical history, encompassing abnormalities and surgeries reported as occurring before the Screening Visit, will be coded using the Medical Dictionary for Regulatory Activities (MedDRA), version 19.0 or newer. Unique participants who report medical history events will be summarized by MedDRA system organ class (SOC) and preferred term (PT) in total and by cohort (PK cohort and Non-PK cohort) for the Safety Population as follows:

Table 5-7 Medical History Summary

Parameter	Description	Timing	Methodology
Medical history	Abnormalities and surgeries occurring	Screening Period	Categorical
	before the Screening Visit		descriptives

SOCs will be sorted alphabetically; PTs will be sorted in descending frequency in the total group.

5.1.1.2.6 Prior and Concomitant Medications

Medications will be coded using the World Health Organization (WHO) Drug Dictionary Enhanced (DDE), version MAR2016 or newer. Unique participants who reported medications will be summarized by Anatomical Therapeutic Chemical (ATC) 4 class and PT in total and by cohort (PK cohort and Non-PK cohort) for the Safety Population as follows:

Table 5-8 Medication Summaries

Parameter	Description	Timing	Methodology
Prior medications ¹	Medications taken ≥ 1 time before the	Screening Period	Categorical
	study treatment start date, regardless of		descriptives
	medication end date		_
Concomitant	Medications taken ≥ 1 time on or after the	Treatment Period	Categorical
medications ¹	study treatment start date, regardless of		descriptives
	medication start date		

ATC4 classes will be sorted alphabetically; PTs will be sorted in descending frequency in the total group.

5.1.1.3 Efficacy Analyses

Efficacy analyses are to be considered exploratory and no inferential statistics will be presented for this study. Efficacy analyses will be based on the mITT Population.

The following efficacy assessments and terms are defined:

¹ If the available date information is not sufficient for classification, the medication will be classified as both a prior medication and a concomitant medication.

Table 5-9 Efficacy Assessments

Assessment/Term	Description		
Investigator's Global	Overall severity of acne vulgaris evaluated using a 5-point IGA (face only):		
Assessment (IGA)	• Clear (0)		
	 No comedones, papules or pustules 		
	 Residual hyperpigmentation and erythema may be present 		
	• Almost clear (1)		
	o Rare comedones		
	 No more than a few small papules and pustules 		
	• Mild (2)		
	 Easily recognizable comedones in limited numbers 		
	 +/- Presence of small papules and pustules 		
	Moderate (3)		
	 Many comedones 		
	 +/- Easily recognizable small and medium-sized papules 		
	 No nodules or cysts. 		
	• Severe (4)		
	 Widespread and numerous comedones 		
	 Many small, medium-sized and large papules and pustules 		
	 Nodules or cysts may or may not be present. 		
Inflammatory lesion counts	Inflammatory lesion counts will be the sum of counts of the following lesion types		
	(face only):		
	• Papule – a small, red, solid elevation less than 1.0 cm in diameter		
	• Pustule – a small, circumscribed elevation of the skin that contains yellow-		
	white exudate		
	• Nodule – a circumscribed, elevated, solid lesion generally more than 1.0		
	cm in diameter with palpable depth		
	 Cyst – a smooth, dome-shaped, elevated, freely moveable, skin colored, 		
	round to ovoid lesion greater than 0.7 cm in diameter		
Noninflammatory lesion	Noninflammatory lesion counts will be the sum of counts of the following lesion		
counts	type (face only):		
	• Open Comedone – a pigmented dilated pilosebaceous orifice (blackhead)		
	Closed Comedone – a tiny white papule (whitehead)		
Total lesion counts	Total lesion counts will be the sum of inflammatory lesion counts and		
	noninflammatory lesion counts (face only).		

Baseline assessments for IGA and lesion count will be the latest assessment pre-treatment on or before day 1 (visit 2).

The efficacy endpoints will be summarized in total (both study cohorts combined) as follows:

Table 5-10 Efficacy Analyses

Endpoint	Description	Timing	Methodology
IGA	Summary by analysis visit: • Proportion of patients with none (0) or minimal (1) score • Proportion of patients with none (0) or minimal (1) score plus at least a 2-grade improvement from baseline	Baseline (day 1), and Weeks 1, 2, 4, 8, and 12/early exit	Categorical descriptives
Inflammatory lesion	Summary by analysis visit:	Baseline (day 1),	CFB descriptives
counts ¹	Change from baseline	and Weeks 1, 2, 4,	

Endpoint	Description	Timing	Methodology
	 Percent change from baseline 	8, and 12/early exit	
Noninflammatory lesion	Summary by analysis visit:	Baseline (day 1),	CFB descriptives
counts ¹	 Change from baseline 	and Weeks 1, 2, 4,	
	 Percent change from baseline 	8, and 12/early exit	
Total lesion counts	Summary by analysis visit:	Baseline (day 1),	CFB descriptives
	 Change from baseline 	and Weeks 1, 2, 4,	
	 Percent change from baseline 	8, and 12/early exit	

¹ If a number of patients have fewer than 5 inflammatory or noninflammatory lesions at baseline, an additional analysis may be conducted for that lesion type including only those patients with at least 5 lesions of that type at baseline.

5.1.1.4 Pharmacokinetic Analyses

The PK analysis plan is beyond the scope of this document and will be outlined in a separate document.

5.1.1.5 Safety Analyses

Safety analyses will be based on the Safety Population.

5.1.1.5.1 Study Treatment Exposure and Compliance

Study treatment exposure and compliance will be summarized in total and by cohort (PK cohort and Non-PK cohort) for the Safety Population as follows:

Table 5-11 Study Treatment Summaries

Parameter	Description	Timing	Methodology
Study treatment	Treatment end date - treatment start date + 1	Treatment Period	Continuous
exposure (days)			descriptives
Mean daily dose for	For PK cohort only, summary by visit	Baseline (day 1)-	Continuous
PK cohort	interval:	Week 1 (visit 2-3);	descriptives
		Week 1–4 (visit 3-5);	
	Weight of study drug dispensed -	Week 4–8 (visit 5-6);	
	Weight of study drug returned	Week 8–12 (visit 6-7)	
	Interval duration ¹	Treatment Period	
Mean daily dose for	For Non-PK cohort only, summary by visit	Baseline (day 1)-	Continuous
non-PK cohort	interval:	Week 4 (visit 2-5);	descriptives
		Week 4–8 (visit 5-6);	
	Weight of study drug dispensed -	Week 8–12 (visit 6-7)	
	Weight of study drug returned	Treatment Period	
	Interval duration ¹		
Study treatment	Summary by visit interval and by cohort (PK	Baseline (day 1)-	Continuous
compliance (%)	cohort and Non-PK cohort):	Week 1 (visit 2-3),	descriptives
		Week 1–2 (visit 3-4),	
	Number of days treatment	Week 2–4 (visit 4-5),	
	100 × taken as prescribed ²	Week 4–8 (visit 5-6),	
	Interval duration ¹	Week 8–12 (visit 6-7)	
		Treatment Period	

¹ Interval duration=Interval end date – interval start date + 1, for the visit interval starting from baseline (day 1).

² An individual usage tube containing 2 grams of study drug is expected for PK cohort in the first 8 (+2) days; otherwise, an approximately pea-sized amount of study drug is expected. Number of days treatment taken as prescribed = interval duration – number missed – number extra during interval.

5.1.1.5.2 Adverse Events

The following adverse event (AE) terms are defined:

Table 5-12 AE Terms

Term	Description
Treatment-	An adverse event recorded on the eCRF would be considered treatment-emergent if either of
emergent adverse	the following conditions are met:
event (TEAE)	AE onset date ≥ first study treatment date; or
	AE onset date < first study treatment date and either:
	• the severity of the event worsened on or after the first study treatment date, or
	the event became serious on or after the first study treatment date
Serious	An event identified as TEAE that further meets serious adverse event (SAE) criteria at any
Treatment-	time would be a treatment-emergent SAE.
emergent adverse	
event (TEAE)	

AEs, encompassing abnormalities and surgeries reported as occurring after the Screening Visit, will be coded using MedDRA version 19.0 or newer. Unique participants reporting AEs in the following AE categories will be summarized in total and by cohort (PK cohort and Non-PK cohort) for the Safety Population as follows:

Table 5-13 AE Summaries

Parameter	Description	Timing	Methodology
Overall summary	Overall summary only for the following categories:	From treatment start date until Week 12 or early termination date, whichever comes first	Categorical descriptives
TEAEs	Overall summary and by SOC and PT	From treatment start date until Week 12 or early termination date, whichever comes first	Categorical descriptives
TEAEs by severity	Overall summary and by SOC, PT and worst severity The worst severity is defined as the greater of the onset severity and maximum severity following onset recorded on the eCRF. If the same TEAE term has been reported more than once for a subject with different severity grades, the worst severity grade will be used in the tabulation.	From treatment start date until Week 12 or early termination date, whichever comes first	Categorical descriptives
Treatment-related TEAEs	Overall summary and by SOC and PT	From treatment start date until Week 12 or early termination date, whichever comes first	Categorical descriptives

Parameter	Description	Timing	Methodology
Treatment-related	Overall summary and by SOC, PT and	From treatment start	Categorical
TEAEs by severity	worst severity	date until Week 12 or	descriptives
		early termination date,	
	The worst severity is defined as the greater	whichever comes first	
	of the onset severity and maximum severity		
	following onset recorded on the eCRF. If		
	the same TEAE term has been reported		
	more than once for a subject with different		
	severity grades, the worst severity grade		
C. C. TEAE	will be used in the tabulation.	F	Catalania
Serious TEAEs	Overall summary and by SOC and PT	From treatment start date until Week 12 or	Categorical
		early termination date,	descriptives
		whichever comes first	
TEAEs leading to study	Overall summary and by SOC and PT	From treatment start	Categorical
discontinuation	Overall summary and by SOC and 1 1	date until Week 12 or	descriptives
discontinuation		early termination date,	descriptives
		whichever comes first	
Common TEAEs	Summary by SOC and PT	From treatment start	Categorical
	 Includes TEAEs occurring in ≥ 	date until Week 12 or	descriptives
	5% of participants in either PK	early termination date,	1
	cohort or Non-PK cohort	whichever comes first	

SOCs will be sorted alphabetically; PTs will be sorted by descending proportions in the total group.

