### 7.3.1 Safety Analyses

Safety variables are treatment-emergent adverse events (TEAEs), including new findings from physical examinations, local (dermal) tolerability, and vital signs.

All adverse events will be coded from the verbatim text to the lower level term and mapped to preferred term (PT) and primary system organ class (SOC) using the Medical Dictionary for Regulatory Activities (MedDRA).

All TEAEs will be listed by patient. For TEAEs regardless of causality, and for treatment-related TEAEs, the number and percentage of patients reporting the TEAEs at least once will be tabulated by descending order of incidence rate by PT within primary SOC, and by primary SOC, PT, and severity.

Local (dermal) tolerability data will be summarized using descriptive statistics and frequency distributions. Vital signs will be summarized using descriptive statistics. Positive pregnancy test results will be listed.

More detailed analyses for the safety measures will be described in the analysis plan.

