### 9.3 Procedures for Reporting a Serious Adverse Event

Any serious adverse event occurring during the study period (beginning with informed consent) and for at least 28 days after the last dose of study drug must be immediately reported but no later than 24 hours after learning of a serious adverse event. Serious adverse events must be reported to the Sponsor (or Agent of the Sponsor) as listed on the Sponsor's Study Contacts Page and recorded on the serious adverse event form. All patients with a serious adverse event must be followed up and the outcomes reported. The investigator must supply the sponsor and the IRB/IEC with any additional requested information (eg, autopsy reports and discharge summaries).

In the event of a serious adverse event, the investigator must:

1. Notify the Sponsor immediately by fax or email using the serious adverse event form (contact details can be found on page 1 of the serious adverse event form); phone numbers and relevant Sponsor personnel contacts are also on the front page of protocol and Study Contacts Page.
2. Obtain and maintain in his/her files all pertinent medical records, information, and medical judgments from colleagues who assisted in the treatment and follow-up of the patient.
3. Provide the Sponsor with a complete, written description of the adverse event(s) on the serious adverse event form describing the event chronologically, including any treatment given (eg, medications administered, procedures performed) for the adverse event(s). Summarize relevant clinical information about the event: signs, symptoms, diagnosis, clinical course and relevant clinical laboratory tests, etc. Include any additional or alternative explanation(s) for the causality which includes a statement as to whether the event was or was not related to the use of the investigational drug.

GDD-TA-T-004 v2015.10

4. Promptly inform the governing IRB/IEC of the serious adverse event as required by the IRB/IEC, local regulations, and the governing health authorities.

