6.2.2 Safety

The analysis visit windows for safety endpoints are defined as follows (note that not all safety endpoints are collected at each visit):

Table 6-3 Safety Analysis Visit Definitions

Analysis Phase	Analysis Visit (Derived)	Study Visit (eCRF)	Window
Pretreatment	Baseline	Day 1/Visit 2	Treatment Day ≤ 1

Analysis Phase	Analysis Visit (Derived)	Study Visit (eCRF)	Window
Treatment	Week 1	Day 8/Visit 3	Treatment Day [6, 11]
	Week 2	Day 15/Visit 4	Treatment Day [12, 21]
	Week 4	Day 29/Visit 5	Treatment Day [22, 42]
	Week 8	Day 57/Visit 6	Treatment Day [43, 70]
	Week 12	Day 85/Visit 7	Treatment Day [71, last dose + 14
			days]

Local dermal tolerability data will be collected both pre-dose and post-dose at day 1 (visit 2)

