6.3.3 Missing/Incomplete AE/Medication End Date

AE and medication end dates will be imputed as the minimum of the following:

- Initial imputed date, where target date = Treatment end date + 28
- Death date

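### Table 5-13 ends the Serious TEAE summary at Week 12 or early termination, while Table 5-12 and the protocol's SAE reporting period both run past exit

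*SAP*

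**What the plan says.** SAP 5.1.1.5.2 defines the terms in Table 5-12 and the summaries in Table 5-13.

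- **Definition.** The first condition for a TEAE is "AE onset date ≥ first study treatment date; or". The alternative covers events that began before treatment and then worsened or became serious. Neither condition has an end date. A serious TEAE is a TEAE that meets the SAE criteria at any time.
- **Summaries.** Each row of Table 5-13 has the timing "From treatment start date until Week 12 or early termination date, whichever comes first". The Serious TEAEs row carries the same entry, beginning "From treatment start date until Week 12 or".
- **Reporting period.** Protocol 9.3 requires that an SAE occurring from consent onward and "for at least 28 days after the last dose of study drug must be immediately reported".
- **Protocol analysis.** Protocol 7.3.1 says that "the number and percentage of patients reporting the TEAEs at least once will be tabulated", with no end date, and that "All TEAEs will be listed by patient".
- **Last visit.** Protocol 8.4.5 places Week 12/Early Exit at Day 85, plus or minus 7 days. No scheduled visit follows.

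**The concern.** For a patient dosed to exit, the whole 28-day SAE reporting period falls after the last visit. An SAE starting 10 days after exit must be reported and meets the Table 5-12 definition of a serious TEAE. The date range in Table 5-13 would nevertheless exclude it from the Serious TEAE count.

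Safety and tolerability is the first study objective. With about 100 patients, a single SAE is about one percentage point and could turn a tabulated zero into a one. If the range is applied, the mismatch can act in one direction only: it lowers the serious count. Two programmers, one working from Table 5-12 and one from Table 5-13, could produce different counts from the same data.

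**Working it through.** The plan gives no figure to reproduce. The check sets the passages side by side and then counts days.

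**Is the event in or out?** Take an SAE with onset 10 days after exit in a patient whose last dose was on the exit day.

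| Source | Rule | Result |
|---|---|---|
| Protocol 9.3 | within 28 days of last dose | must be reported |
| SAP Table 5-12 | onset on or after first treatment, no upper limit | serious TEAE |
| Protocol 7.3.1 | TEAEs listed by patient | listed |
| SAP Table 5-13, Serious TEAEs | ends at Week 12 or early termination | not counted, if the range is applied |

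**How many days are uncovered?** With the actual exit visit as cut-off:

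uncovered days = max(0, last dose day + 28 − exit day)

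| Exit day | Last dose day | Reporting period ends | Uncovered days |
|---|---|---|---|
| 78 | 78 | 106 | 28 |
| 85 | 85 | 113 | 28 |
| 85 | 84 | 112 | 27 |
| 92 | 84 | 112 | 20 |
| 30 (early) | 30 | 58 | 28 |
| 30 (early) | 20 | 48 | 18 |
| 30 (early) | 2 | 30 | 0 |

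The maximum is 28 days. The gap closes only if dosing stopped 28 days or more before exit.

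**Does another section close the gap?** The Week 12 safety window in SAP 6.2.2, Table 6-3, is "Treatment Day [71, last dose + 14" (days). It assigns assessments to visits and is not stated to govern AE periods. If it were borrowed as the cut-off, 28 − 14 = 14 days would remain uncovered. No other passage extends the serious table past exit.

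**How many events?** The documents give no SAE rate. As an assumption only, take 1 to 5 SAEs per 100 patient-years, 100 patients and the full 28 days for each:

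- Exposure: 100 × 28/365.25 = 7.67 patient-years.
- Expected SAEs: 7.67 × 0.01 = 0.08, to 7.67 × 0.05 = 0.38.
- Chance that none falls in the gap: exp(−0.077) = 93%, to exp(−0.383) = 68%.

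Because 28 days is the maximum per patient, these expected counts are upper values for the assumed rates.

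**The case against.** The strongest reply is that the Timing column does not select events by onset date. In SAP Table 5-7 the column reads Screening Period for medical history that predates the Screening Visit. Table 5-8 uses the same label for medications taken before treatment start. In those tables it seems to mark when data are collected. A strict onset filter beginning at treatment start would also remove the TEAEs that Table 5-12 admits with onset before treatment, which cannot be intended. The SAP never says that the column filters, and SAP Section 4 places the table specifications in a separate document that is not available here.

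This stands as a reason for caution about what will be programmed, but it does not remove the problem. Table 5-13 does not use a period label; it gives a start, an end and a rule for choosing between two end dates. If that range is not meant to select events, the SAP should say so, because the tables as they stand disagree.

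A second reply is that a reporting duty need not set a tabulation period. Events after the last visit come to light without scheduled questioning, so keeping them out of on-study incidence tables is defensible. That is a fair argument for leaving the other rows alone. For SAEs, reporting is mandatory throughout the 28 days, so the data are expected to exist, and the SAP text provides no summary of them.

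A third reply is that such events are not lost. That is correct: Protocol 9.3 requires reporting and follow-up, and Protocol 7.3.1 requires a listing.

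**Conclusion.** Wrong as written, as an internal inconsistency of low impact. Applied literally, Table 5-13 omits from the serious count an event that Table 5-12 defines as a serious TEAE and that Protocol 9.3 requires to be reported. Up to 28 days per patient are uncovered. On the assumed rates, 0.08 to 0.38 events are expected in the gap. No inferential safety test is planned that this could change.

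A reader might infer more, and the documents do not support it:

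- **A gap of 35 days.** This requires a cut-off at nominal Day 85 with dosing until a Day 92 visit (92 + 28 − 85 = 35). The protocol limits treatment to 12 weeks, and nothing says that Week 12 here means nominal Day 85. Paired with an early termination date, it more naturally means the Week 12/Early Exit visit.
- **That the SAP expects new events after exit.** SAP 6.3.3 uses "Initial imputed date, where target date = Treatment end date + 28", but only for missing end dates, for AEs and medications alike. It shows that events may continue after treatment, not that new ones were expected.
- **That the shorter period is hidden.** The range is printed in Table 5-13, and SAP 5.1 says that the SAP text goes into the study report. Titles and footnotes of the final tables cannot be judged from what is available.
- **That a protocol analysis commitment is broken.** Protocol 7.3.1 gives no end date and does not call for a separate serious table.

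**What to change.** 1. State in SAP 5.1.1.5.2 that the on-study TEAE tables end at the actual Week 12/Early Exit visit date, and say whether the Timing column selects events.
2. Then do one of the following:
   - Extend the Serious TEAEs row to all SAEs reported through at least 28 days after the last dose, and treat any serious category in the overall summary the same way (its category list is not in the available text). Footnote that the row covers a longer period than the others and that no scheduled visit follows Week 12.
   - Keep the row as it is and add one table of SAEs with onset after exit.
3. Leave Table 5-12 without an upper onset limit, because the 28 days in Protocol 9.3 are a minimum.

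The cost is one sentence plus either a timing entry with a footnote or one short table. No visits or assessments are added. The downside is a possibly slightly less favourable SAE count and, under the first option, unequal periods across rows.
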